5.1.2 Additional study treatment

Continuation of the concomitant administration of NSAIDs as prescribed before inclusion into the trial is planned beyond the investigational treatment to evaluate the extent of NSAID sparing effect of Secukinumab in this trial.

5.2 Treatment arms

Patients will be assigned to one of the following three treatment arms in a ratio of 1:1:1.

- **Group 1:** Secukinumab 150 mg s.c. at Week 0, 1, 2, 3, 4, 8, 12, 16 and 20; Placebo injections at Week 5, 6, 7 and 17, 18, 19 to maintain the blind for the initial treatment assignment
- **Group 2:** Placebo at Weeks 0, 1, 2, 3 followed by Secukinumab 150 mg s.c. at Week 4, 5, 6, 7, 8, 12, 16 and 20 with Placebo at Week 17, 18, 19 to maintain the blind for the initial treatment assignment
- **Group 3:** Placebo at Weeks 0, 1, 2, 3, 4, 5, 6, 7, 8 and 12. From Week 16, patients will be switched to receive Secukinumab 150 mg s.c. at Week 16, 17, 18, 19, and 20

5.3 Treatment assignment, randomization

At baseline visit, all eligible patients will be randomized via Interactive Response Technology (IRT) to 1 of the treatment arms. The investigator or his/her delegate will contact the IRT after confirming that the patient fulfills all the inclusion/exclusion criteria. The IRT will assign a randomization number to the patient, which will be used to link the patient to a treatment arm and will specify a unique medication number for the first package of investigational treatment to be dispensed to the patient. The randomization number will not be communicated to the caller.

From Week 16 onwards, all patients will receive Secukinumab 150 mg. Those patients originally randomized to placebo will self-inject Secukinumab 150 mg after Week 16 at Week 17, 18, 19 and 20, while patients originally randomized to either of the Secukinumab groups will receive their next Secukinumab injection at Week 20 with Placebo injections at weeks 17, 18, 19 to maintain the blinding of initial treatment assignment.

The randomization numbers will be generated using the following procedure to ensure that treatment assignment is unbiased and concealed from patients and investigator staff. A patient randomization list will be produced using a validated system that automates the random assignment of patient numbers to randomization numbers. These randomization numbers are linked to the different treatment arms, which in turn are linked to medication numbers. A separate medication list will be produced by or under the responsibility of Novartis Biometry using a validated system that automates the random assignment of medication numbers to packs containing the investigational drug(s).

Original treatment assignment, as per baseline randomization, will remain double-blinded to the patient, investigator, and site personnel until after the Week 24 database lock and analyses.

5.4 Treatment blinding

This is a double-blind randomized treatment trial. However, after completion of Week 16 assessments of the primary endpoint, patients initially randomized to placebo will be switched to receive Secukinumab 150 mg s.c. every week with intermittent placebo injections in both active arms at weeks 17, 18, 19 to maintain the blind for the initial treatment assignment.

Until the end of the trial, all original randomized treatment assignments will be double-blinded to patients, investigators, and site personnel.

Unblinding of treatment dose or original randomized treatment assignment will only occur in the case of patient emergencies (see Section 5.5.12).

The hsCRP results from samples collected during the treatment period will not be revealed to the site.

5.5 Treating the patient

5.5.1 Patient numbering

Each patient is uniquely identified in the study by a combination of his/her center number and patient number. The center number is assigned by Novartis to the investigative site. Upon signing the informed consent form, the patient is assigned a patient number by the IRT. Upon signing of the ICF by the patient, the investigator or his/her staff will contact the IRT and provide the requested identifying information for the patient to register them into the IRT. Only the assigned patient number should be entered in the field labeled "Patient ID" on the EDC data entry screen. Once assigned to a patient, the Patient ID will not be reused. If the patient fails to be randomized for any reason, the IRT must be notified within 2 days that the patient was not randomized. The reason for not being randomized will be entered on the Screening Log, and the Demography eCRF should also be completed.

5.5.2 Dispensing the investigational treatment

Each study site will be supplied by Novartis with study treatment in packaging of identical appearance.

The study treatment packaging for Secukinumab/placebo has a 2-part label. A unique medication number is printed on each part of this label. Investigator staff will identify the investigational treatment package(s) to dispense to the patient by contacting the IRT and obtaining the medication number(s).

5.5.3 Handling of study treatment

5.5.3.1 Handling of investigational treatment

Study treatment must be received by a designated person at the study site, handled and stored safely and properly, and kept in a secured location to which only the investigator and designees have access. Upon receipt, all investigational treatment should be stored according to the instructions specified on the labels. Clinical supplies are to be dispensed only in accordance with the protocol. Technical complaints are to be reported to the respective Novartis CPO Quality Assurance.

Medication labels will be in German and comply with the legal requirements of Germany. They will include storage conditions for the study treatment but no information about the patient except for the medication number. The PFS (150 mg active/placebo) sealed in an outer box must be stored in a access controlled/locked refrigerator between 2°C and 8°C and protected from light. They must be carefully controlled in accordance with regulations governing investigational medicinal products and local regulations. The investigator must maintain an accurate record of the shipment and dispensing of study treatment in a drug accountability log. Monitoring of drug accountability will be performed by monitors during site visits or remotely and at the completion of the trial. Patients will be asked to return all unused study treatment and packaging at the end of the study or at the time of discontinuation of study treatment.

At the conclusion of the study, and as appropriate during the course of the study, the investigator will return all unused study treatment, packaging, drug labels, and a copy of the completed Drug Accountability log to the Novartis monitor or to the Novartis address provided in the investigator folder at each site.

Destruction of the unused drug should be done according to local requirements and after approval by Novartis/CRO clinical team.

5.5.3.2 Handling of other study treatment

Not applicable.

5.5.4 Instructions for prescribing and taking study treatment

Study treatment (150 mg Secukinumab and placebo) will be administered s.c. by 1 mL PFS throughout the study as 1 mL/150 mg Secukinumab or 1 mL placebo, respectively. Administration of study treatment will occur via self-injection by the patient from Baseline through to Week 20. Administration of study treatment must occur after the study assessments for the visit have been completed. The PFS with the ready-to-use study treatment solution will be provided by the site staff to the patient. Detailed instructions on the self-administration of the study treatment will be described in the IFU for Secukinumab and provided to each patient.

At the Baseline visit, patients will be instructed by the site staff, utilizing the IFU, on how to self-inject using a PFS. Patients will be asked to raise questions, if they have any, and then to proceed with self-injection. At the Week 1 visit, patients will be asked to refer to the IFU and to proceed directly with self-injection of the study drug (i.e. no prior retraining) for the remainder of the trial. However, if the patient is not comfortable self-injecting the study treatment, then the site staff may administer it for the patient.

All kits of study treatment assigned by the IRT will be recorded in the IRT.

The investigator should promote compliance by instructing the patient to take the study treatment exactly as prescribed and by stating that compliance is necessary for the patient's safety and the validity of the study. The patient should be instructed to contact the investigator if he/she is unable for any reason to take the study treatment as directed.

Subcutaneous administration with pre-filled syringe (PFS)

Secukinumab solution for s.c. injection (150 mg in 1 mL active/placebo) will be provided in a PFS.

The study treatment solution must be injected into normal areas of the skin.

Patients will be instructed by the site staff on how to self-inject study treatment using a PFS, following the IFU. After training at the Baseline visit, the injections will be self-administered into an appropriate site of the body (thighs, arms, abdomen), and each injection should be given at a different injection site to reduce the risk of injection reaction. Each new injection should be given at least 2.5 cm from the previously used site. If the patient chooses the abdomen, the area 5 cm around the navel should be avoided. Investigational drug should not be injected into areas where the skin is tender, bruised, red, or hard, or where patient has scars or stretch marks. Injection sites should be rotated among appropriate sites to reduce the risk of injection reactions.

The PFSs with study treatment solution should be kept at 2 to 8°C, protected from light and should not be stored frozen. Prior to administration the boxes containing the PFSs with study treatment solution should be allowed to come to room temperature unopened for about 20 minutes before administration. Used PFSs should be disposed immediately after use in a sharps container or according to the regulatory needs of the respective countries.

Any PFS for which a defect or malfunction is noticed prior to or during the injection at any of the study visits must be kept at the site until guidance is received from Novartis/CRO on whether it should be returned to Novartis/CRO for investigation or discarded. Devices identified as defective should be stored according to local guidelines, until specific instruction is discussed with Novartis/CRO personnel. Additionally, from baseline onwards, any noticed defect, malfunction, problem during the injections or product complaints with the PFS should be recorded in the source document. Sites should detail the issue, the date, the kit number and the visit number. The site will be asked to record, based on their judgment, whether the observed issue was primarily related to the device or to the user. Device malfunctions should also be immediately reported to Novartis/CRO personnel as a necessary replacement kit may need to be provided.

5.5.5 Permitted dose adjustments and interruptions of study treatment

Investigational treatment dose adjustments are not permitted.

Investigational treatment interruption is only permitted if, in the opinion of the investigator, a patient is deemed to be placed at a significant safety risk unless administration of investigational treatment is temporarily interrupted. In such cases study treatment should be interrupted only during the time that this risk is present and ongoing. Investigational treatment can be restarted at the next scheduled visit after resolution of the safety risk.

The effect of Secukinumab on live vaccines is unknown; therefore live vaccines should not be administered during participation in the study. In case a live vaccine has been administered due to a medical urgency, study treatment should be interrupted for 12 weeks.

Any study treatment interruption must be recorded on the Dosage Administration Record eCRF.

5.5.6 Rescue medication

Rescue medication is defined as any new therapeutic intervention or a significant change to ongoing therapy made because a patient is experiencing either no benefit from participation in the trial or worsening/exacerbation of their disease. Rescue medication must not be used before completion of Week 12 assessments. Although no patient will be restricted from receiving necessary rescue medications for lack of benefit or worsening of disease, if rescue with prohibited biologics (as described in Section 5.5.8) occurs, patients will be discontinued from the study and enter into the follow-up period after an end of study visit. Efficacy will be assessed in detail at every study visit, and patients who are deemed not to be benefiting from the study treatment based upon safety and efficacy assessments by the investigator or for any reason on their own accord will be free to discontinue the study at any time. Changes in NSAID concomitant therapy are permitted after Week 4 assessments and should ideally be performed according to the non-binding NSAID tapering guidelines provided to the patient at the week 4 visit. Please see Section 5.5.7 and Section 5.5.8 for details.

Use of rescue medication must be recorded on the Prior and Concomitant medications in the eCRF page.

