- 11. To demonstrate that the efficacy of Secukinumab 150 mg s.c. at week 12 is superior to placebo based on the change from baseline in health-related Quality of Life as measured by the SF-36 PCS.
- 12. To demonstrate that the efficacy of Secukinumab 150 mg s.c. (Secukinumab from week 0 with NSAID tapering allowed from week 4; "delayed tapering") at Week 12 is superior to placebo based on the change from baseline in health-related Quality of Life as measured by the SF-36 PCS.
- 13. To demonstrate that the efficacy of Secukinumab 150 mg s.c. (Secukinumab from week 4 with NSAID tapering allowed from week 4; "early tapering") at Week 12 is superior to placebo based on the change from baseline in health-related Quality of Life as measured by the SF-36 PCS.
- 14. To compare between both Secukinumab regimens concerning the change from baseline in ASAS-NSAID score after 12 weeks of Secukinumab exposure (ASAS-NSAID index at Week 12 for "delayed tapering" vs. Week 16 for "early tapering").

2.3 **Exploratory objectives**

- 1. To compare between both Secukinumab regimens concerning the change from baseline in the BASDAI after 12 weeks of Secukinumab exposure (BASDAI at Week 12 for "delayed tapering" vs. Week 16 for "early tapering").
- 2. To evaluate change in patient reported neck, back and hip pain (BASDAI question 2; Appendix 4) beginning from Secukinumab treatment on a continuous basis in patients exposed to Secukinumab 150 mg s.c. for 12 weeks vs. placebo.
- 3. To evaluate change in patient reported neck, back and hip pain (BASDAI question 2; Appendix 4) from baseline on a continuous basis in patients randomized Secukinumab 150 mg s.c. (Secukinumab from week 0 with NSAID tapering allowed from week 4; "delayed tapering") vs. placebo from week 0 to week 12.
- 4. To evaluate change in patient reported neck, back and hip pain (BASDAI question 2; Appendix 4) from baseline on a continuous basis in patients randomized Secukinumab 150 mg s.c. (early tapering) vs. placebo from week 0 to week 16.

Amended Protocol Version v01 Clean

- To compare ASAS20 response rates at week 4 in Secukinumab 150 mg. s.c. (Secukinumab from week 0 with NSAID tapering allowed from week 4; "delayed tapering") vs. week 20 in the patients switching from Placebo after 4 weeks of Secukinumab exposure each.
- 6. Total ASAS-NSAID [Area Under Curve (AUC)] Score from treatment start with Secukinumab to a Secukinumab exposure of 12 weeks.

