5.5.7 Concomitant treatment

The investigator should instruct the patient to notify the study site about any new medications he/she takes after the patient was enrolled into the study. All medications, procedures and significant non-drug therapies (including physical therapy and blood transfusions) administered after the patient was enrolled into the study must be recorded on the Prior and Concomitant medications or Procedures and Significant Non Drug Therapy eCRF. The reason, name of the drug, procedure or non-drug therapy should be listed.

Guidelines for the use of specific medications are provided below:

Methotrexate

Patients taking MTX (up to 25 mg/week) must be on a stable dose for at least 4 weeks before randomization and maintained stable until Week 12, except if MTX-related adverse events develop.

Folic acid

Patients on MTX must be taking folic acid supplementation before randomization and during the trial to minimize the likelihood of MTX associated toxicity.

Leflunomide wash-out with cholestyramine

In case of leflunomide treatment, a drug wash-out of 8 weeks has to be performed; however, another wash-out procedure may be considered. Cholestyramine could be given orally to washout the drug at a dose of 8 g t.i.d. Cholestyramine reduced plasma levels of the active leflunomide metabolite by approximately 40% in 24 hours and by 49% to 65% in 48 hours in 3 healthy volunteers. The administration of cholestyramine is recommended in patients who require a drug elimination procedure. If a patient receives 8 g t.i.d. for 11 days he/she could be safely randomized 4 weeks after the beginning of the 11- day treatment period.

Systemic corticosteroids

Treatment with systemic corticosteroids is permitted up to a maximum daily dose of 10 mg prednisone equivalent and if the dose was stable within the 2 weeks preceding randomization.

Corticosteroid dose reductions below 10 mg prednisone equivalent are permitted after Week 12. although the corticosteroid dose should not be reduced by more than 1 mg prednisone equivalent every 4 weeks.

After Week 12, the dose and regimen of systemic corticosteroids may be modified as per investigator's judgment and patient need.

Any change in the dose of systemic corticosteroids during the trial must be recorded on the corresponding eCRF page.

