Intra-articular corticosteroids are not permitted within the 4 weeks preceding randomization and up to Week 12. After Week 12, no more than 1 joint per 24-week period may be injected. No single injection should exceed 40 mg of triamcinolone (or equivalent) and the total dose of intra-articular corticosteroid may not exceed 80 mg of triamcinolone (or equivalent) during any 20-week period. Injection of intra-articular steroids is not permitted within 8 weeks prior to Week 20.

Non-steroidal anti-inflammatory drugs (NSAIDs) (including COX-1 or COX-2 inhibitors), low strength opioids and acetaminophen/paracetamol

Patients regularly using NSAIDs, low strength opioids, or paracetamol/acetaminophen should be on stable dose for at least 2 weeks before randomization to allow inclusion. They should remain on a stable dose in the study up to Week 4.

Changes in the NSAID intake will be captured by the patient in the patient diary and checked and be transferred into the eCRF at all scheduled study visits after week 4.

Patients taking low strength opioids or paracetamol/acetaminophen PRN within the 2 weeks before randomization can continue to do so in the study; however, they have to refrain from any intake during at least 24 hours before a visit with disease activity assessment.

After Week 12 assessments are completed, a change in the low strength opioids, or paracetamol/acetaminophen treatment regimen is permitted.

Any change of the low strength opioids, or paracetamol/acetaminophen treatment during the trial should be recorded on the appropriate Prior and Concomitant medication eCRF page.

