5.5.8 Prohibited treatment

Use of the treatments displayed in Table 5-1 is NOT allowed after the start of the washout period unless otherwise specified below.

Live vaccines should not be given until 12 weeks after last study treatment administration.

Table 5-1	Prohibited treatment
i able 5- i	Prombiled freatment

Prohibited treatments	Washout period (before randomization)
Etanercept*	4 weeks
Infliximab*	8 weeks
Adalimumab, golimumab, certolizumab*	10 weeks
Unstable dose of MTX or sulfasalazine (until Week 12)	4 weeks
Other DMARD (except MTX or sulfasalazine)	4 weeks
Leflunomide	8 weeks
Leflunomide with cholestyramine washout	4 weeks
Systemic corticosteroids > 10 mg prednisone equivalent** (until Week 12)	2 weeks
Intra-articular steroids injections (until Week 12)	4 weeks
Any investigational treatment or participation in any interventional trial	4 weeks or 5 half-lives (whichever is longer)
Analgesics other than paracetamol/acetaminophen or low strength opioids PRN	4 weeks
Live vaccinations	6 weeks

^{*}These agents fall under the category of biologic immunomodulators and are prohibited medications. Administration of these agents requires study discontinuation (see Section 5.5.8).

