#### Secondary objectives:

- H2: Secukinumab 150 mg s.c. (pooled Secukinumab groups) is not different to placebo regimen with respect to change from baseline in ASAS-NSAID score at Week 12
- H3: Secukinumab 150 mg s.c. (pooled Secukinumab groups) is not different to placebo regimen with respect to change from baseline in total BASDAI score at Week 12
- H4: Secukinumab 150 mg s.c. (delayed tapering) is not different to placebo regimen with respect to signs and symptoms (ASAS20 response) at Week 12
- H5: Secukinumab 150 mg s.c. (early tapering) is not different to placebo regimen with respect to signs and symptoms (ASAS20 response) at Week 12
- H6: Secukinumab 150 mg s.c. (early tapering) is not different to placebo regimen with respect to signs and symptoms (ASAS20 response) at Week 16.
- H7: Secukinumab 150 mg s.c. (delayed tapering) is not different to placebo regimen with respect to change from baseline in ASAS-NSAID score at Week 12.
- H8: Secukinumab 150 mg s.c. (early tapering) is not different to placebo regimen with respect to change from baseline in ASAS-NSAID score at Week 12.
- H9: Secukinumab 150 mg s.c. (delayed tapering) is not different to placebo regimen with respect to change from baseline in total BASDAI score at Week 12.
- H10: Secukinumab 150 mg s.c. (early tapering) is not different to placebo regimen with respect to change from baseline in total BASDAI score at Week 12
- H11: Secukinumab 150 mg s.c. (early tapering) is not different to placebo regimen with respect to change from baseline in total BASDAI score at Week 16.

These hypotheses will in principal be tested hierarchically in ascending order. However, since some hypotheses for individual group comparisons are already contained in the higher-ranked, pooled comparisons for the same endpoint (i.e. H4 and H5 are contained in H1, H7 and H8 are contained in H2 and H9 and H10 are contained in H3) these individual hypothesis can be tested simultaneously. The justification is that as soon as the pooled hypothesis has been rejected (e.g. H1), at least one of the two contained individual hypotheses (e.g. H4 and H5) must be false and there is only a potential for at most one type-I-error. Therefore H4 and H5 can be tested simultaneously once all higher-ranked hypotheses have been rejected. The same argument applies to H7 and H8 and to H9 and H10.

The following chart displays the testing strategy graphically:

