### **2.7.3 Handling of missing values/censoring/discontinuations**

Missing data for ASAS20 response and other binary efficacy variables (e.g. ASAS5/6, etc.) for data up to Week 20 will be handled as follows:

1. Subjects who drop out of the trial for any reason will be considered non-responders from the time they drop out through Week 20.
2. Subjects who do not have the required data to compute response (e.g. ASAS components) at baseline and at the specific time point will be classified as non-responders.

Patients who were unblinded prior to the scheduled timepoint will be considered non-responders from the time of unblinding up to Week 16. The secondary analysis will use the non-responder imputation only.

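### Non-biologic rescue is open between Weeks 12 and 16, and the SAP has no rule for it, although H6, H11 and the early-arm equal-exposure readings are taken at Week 16

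*Protocol*

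**What the plan says.** **Restrictions that end at Week 12.**
- Rescue (Protocol 5.5.6): "Rescue medication must not be used before completion of Week 12 assessments".
- Methotrexate (5.5.7): "maintained stable until Week 12, except if MTX-related adverse events develop". Table 5-1 in 5.5.8 lists as prohibited "Unstable dose of MTX or sulfasalazine (until Week 12").
- Systemic corticosteroids (5.5.7): dose and regimen may be modified after Week 12 at the investigator's judgement.
- Low-strength opioids and paracetamol (5.5.7): "After Week 12 assessments are completed, a change in the low strength opioids, or paracetamol/acetaminophen treatment regimen is permitted". The same section also gives Week 4 as the end of the stable-dose period for regular users.

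**Readings at Week 16.** Protocol 3.4 keeps placebo patients unswitched until all Week 16 assessments are done, and SAP 2.1.1 defines Treatment Period 1 as placebo-controlled to Week 16 pre-dose. The SAP hierarchy includes "H6: Secukinumab 150 mg s.c. (early tapering) is not different to placebo regimen with respect to signs and symptoms (ASAS20 response) at Week 16", and H11 is the same contrast for BASDAI. H6 gates H7–H11. Secondary objective 14 is "To compare between both Secukinumab regimens concerning the change from baseline in ASAS-NSAID score after 12 weeks of Secukinumab exposure", with the delayed arm at Week 12 and the early arm at Week 16. Protocol 9.5.2 extends that pairing to the other variables.

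**Scoring.** SAP 2.7.3: "Subjects who drop out of the trial for any reason will be considered non-responders from the time they drop out through Week 20". Missing components and unblinding are also non-response. Continuous variables go into an MMRM under missing at random (Protocol 9.4.3). The title of SAP 2.4 names rescue medication, but no rule follows. Protocol 5.5.6 removes one group only: "if rescue with prohibited biologics (as described in Section 5.5.8) occurs, patients will be discontinued from the study".

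**The concern.** The plan treats Week 16 as the end of the controlled period for placebo, for unblinding and for two confirmatory tests, but not for rescue. Two patients who fail in Week 13 are then handled in opposite ways. One who receives a biologic leaves the study and is a non-responder for H6. One who receives any other rescue stays, is scored on the observed Week 16 value, and can count as a responder.

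Two comparisons are exposed. For H6 and H11, rescue is more likely in patients who are not benefiting, so probably more common on placebo. Successful rescue would raise the placebo result and dilute the effect, and a failed H6 stops confirmatory testing of H7–H11. For early versus delayed, only the early reading follows a period in which rescue is allowed. Effective rescue can therefore favour the early arm even if the two regimens are identical. That contrast bears on when to start tapering, which is a central question of the trial.

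**Working it through.** **Inputs.** Protocol 9.7 and SAP 3 give 56.9% versus 27.0% ASAS20, two-sided 5%, 62 per group and 90% power. The same effect is assumed for early tapering at Week 16. About 190 patients in three arms gives 63 per arm. The rescue share (10% or 20%) and the conversion of half of those rescued are assumptions, because the documents give neither. Rescued patients are taken to be non-responders at the time.

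**Formula.** Power = Φ[(|p1 − p0| − 1.96·SE0)/SE1], with SE0 = √(2p̄(1 − p̄)/n) and SE1 = √([p0(1 − p0) + p1(1 − p1)]/n). The continuity correction subtracts 1/n from |p1 − p0|.

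**The plan's figures first.** At n = 62, (0.299 − 1.96 × 0.0886)/0.0845 = 1.48, so power is 93.1%. Corrected, (0.2829 − 0.1737)/0.0845 = 1.29, or 90.2%, matching the stated 90%. The unequal-allocation analogue with 64 placebo and 126 pooled patients at 35% placebo response gives 77.8% corrected (82.2% uncorrected), matching the stated 78%. The plan's ASAS20 figures are therefore continuity-corrected, and both versions are shown below.

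**H6 with rescue, n = 63.** Observed rate = base rate + rescued share × 0.5. Example with 10% rescue on placebo only: p0 = 0.27 + 0.05 = 0.32, and (0.249 − 1.96 × 0.0885)/0.0857 = 0.88, so power is 81%. The last column is the early-arm gain over a delayed arm with the same true rate, 0.5 × early-arm rescue.

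| Rescue placebo / early | Placebo rate | Early rate | H6 power | Corrected | Gain, early vs delayed |
|---|---|---|---|---|---|
| 0 / 0 | 27.0% | 56.9% | 94% | 91% | 0 |
| 10% / 0 | 32.0% | 56.9% | 81% | 76% | 0 |
| 10% / 5% | 32.0% | 59.4% | 88% | 84% | 2.5 points |
| 10% / 10% | 32.0% | 61.9% | 93% | 90% | 5 points |
| 20% / 0 | 37.0% | 56.9% | 61% | 54% | 0 |
| 20% / 10% | 37.0% | 61.9% | 81% | 75% | 5 points |
| 20% / 20% | 37.0% | 66.9% | 93% | 90% | 10 points |

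The two harms trade off. The rows that hurt H6 most leave early versus delayed untouched, and the reverse also holds. From a 35% placebo rate, H6 starts at 70% (63% corrected) and falls to 48% or 27% with placebo-only rescue, or to 59% or 48% with half the rate in the early arm.

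**H11.** The plan assumes a difference of 1.8 with SD 2.8. At 62 per group and two-sided 5% this gives 95% power; the stated 91% reproduces only at 2.5%. If 20% of placebo patients are rescued and each gains 1 or 2 points (assumed), with none rescued in the early arm, the difference is 1.8 − 0.2 = 1.6 or 1.8 − 0.4 = 1.4. Power is then 89% or 80% at 5%.

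**The case against.** **Using observed data is a legitimate treatment-policy choice.** It can be, and the primary estimand does disregard adherence. But that estimand covers only the Week 12 primary variable and speaks of adherence, not rescue. The plan also does not apply the policy uniformly, since biologic rescue ends in non-response. Neither strategy is stated for Week 16.

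**The power loss rests on invented inputs.** This largely stands. A reader might infer that H6 power drops from 94% to 61%. That needs 20% rescue on placebo and none in the early arm, and it cannot be combined with a 10–20% early-arm rescue rate used to argue bias in early versus delayed. At equal rates the H6 loss disappears.

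**Background therapy is not simply frozen before Week 12 and free afterwards.** This also stands. A reader might infer that the delayed arm is always read under frozen therapy, but NSAIDs may change from Week 4 in every arm, methotrexate may change earlier for adverse events, and the opioid/paracetamol text gives two end points. Other DMARDs and leflunomide carry no Week 12 limit in Table 5-1, and patients taking opioids or paracetamol as needed must abstain for 24 hours before disease-activity visits.

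**The multiplicity claim is not endangered.** Correct. Under a true null, blinded arms should be rescued alike, so inflated type I error for H6 or H11 does not follow. The early-versus-delayed contrasts lie outside H1–H11.

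**Conclusion.** The gap is real and limited. H1–H5 are read at Week 12 and are not affected. H7–H10 are also Week 12 readings and are exposed only through the H6 gate. Observed scoring of non-biologic rescue follows from the absence of any rule; the SAP does not state it as a choice. The deviation list in SAP 5.6 does not close the gap: every item is kept in all analyses, and the methotrexate-change item stops at Week 12.

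For H6 and H11 the likely consequence is dilution and lost power. For H6 at the planned rates this ranges from almost nothing (93% at equal rescue rates) to 61% in the one-sided 20% case, or 90% to 54% with continuity correction. For early versus delayed there is a structural asymmetry, worth 2.5 to 10 points of ASAS20 if 5–20% of early-arm patients are rescued and half convert. All these sizes depend on the assumed rescue share and conversion. No size can be given for objective 14, because the documents do not say how rescue would move the ASAS-NSAID score.

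**What to change.** 1. **SAP 2.7.3.** For Week 16 binary endpoints, count as a non-responder any patient who starts rescue as defined in Protocol 5.5.6 after the Week 12 and before the Week 16 assessment. Limit this to new therapy or a significant change made for lack of benefit or worsening. Do not apply it to changes made for adverse events, to reductions after improvement, or to the NSAID changes the protocol permits. A rule triggered by any change would fail patients who cut analgesics because they improved.
2. **H11 and objective 14.** State the rescue strategy, and add an analysis that leaves post-rescue values out of the MMRM.
3. **Early versus delayed.** Report with and without the rule, because only the early arm can incur it.
4. **Process.** Identify cases from the concomitant-medication eCRF, where rescue is already recorded, blind and before database lock. Tabulate them by arm.
5. **Reconcile.** The sponsor should reconcile the Week 12 end of the restrictions with the Week 16 endpoints. Two conflicts within Protocol 5.5.7 also need resolving: Week 4 against Week 12 for opioids and paracetamol, and intra-articular steroids allowed after Week 12 but barred within 8 weeks before Week 20. Which clinical rule applies is for the sponsor.

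The cost is SAP wording and a blinded medication review. Week 16 response rates will be slightly lower, and the Week 16 effect will count rescue as failure.
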